Brexpiprazole is a newly approved dopamine D₂ receptor partial agonist for schizophrenia treatment. It shows partial agonism with lower intrinsic activity at

the D₂ receptor and stronger antagonism at the 5-HT_{2A} receptor than aripiprazole (10). We hypothesize that brexpiprazole, similar as aripiprazole, can decrease the level of craving and reduce the use of substance in patients with schizophrenia; further, brexpiprazole may be even more efficacious than aripiprazole in reducing substance use given its relatively lower potential to induce D₂ partial agonist-mediated activating adverse effects such as restlessness, insomnia, and nausea (11), which are common substance withdrawal symptoms.

B. RATIONALE AND STUDY DESIGN

The proposed study is a 4-site, 12-week, novel, feasibility, "proof of concept" investigation of patients who have co-occurring diagnoses of schizophrenia and current substance use disorder (alcohol, cocaine, heroin, or cannabis). Fifty patients not treated with aripiprazole or cariprazine (the other two dopamine receptor partial agonists) at the time of consent will be randomly assigned to switch to brexpiprazole (the brexpiprazole group) or remain on the same antipsychotic treatment (the control group).

C. STUDY OBJECTIVES

The primary objectives of the study include:

1) examine the effect of brexpiprazole treatment on the number of days of substance use in the past week as measured by the Timeline Follow-Back (TLFB) assessment;

2) examine the effect of brexpiprazole treatment on substance craving using 100mm visual analogue scale (VAS).

The secondary objectives are to examine the effect of brexpiprazole treatment on:

1) the dollar amount spent on substances in the past week;

2) the psychiatric symptoms as measured by various clinical rating scales;3) quality of life.

Additional objectives of this study include collection of additional safety data on brexpiprazole using safety parameters (ECG, metabolic labs, vital signs, suicidality, EPS, side effects measured by the SAFTEE) throughout the study

D. STUDY POPULATION

The study will be conducted at 4 sites in the US. We expect to enroll 50 subjects across 4 sites. We anticipate a 20% discontinuation for this study. Hence we will randomize 50 subjects so we will have 40 subjects completing the study.

Eligibility Criteria

Inclusion criteria:

Each subject must meet all study inclusion criteria prior to randomization.

- 1) Age 18-65 years old

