Pregnancy Tests: A urine dip stick pregnancy tests will be administered to all women at screening. The pregnancy test can be repeated at any time during the study as per PI discretion. All subjects must test negative for pregnancy tests to be eligible for the study.

Urine Drug Tests: All subjects must undergo urine drug tests for a panel of substances at every study visit. The urine drug test will be completed prior to administering the timeline follow-back (TLFB).

The urine drug screen will include opioids, cocaine, methamphetamines, cannabinoids, barbiturates, benzodiazepines, methamphetamine, and phencyclidine.

Supportive Counseling: Qualified staff will provide supportive counseling to study subjects at weekly visits. Brief supportive counseling sessions about substance use will be provided as part of study visits. The content and structure is adapted

from the Individual Resiliency Training (IRT) manual that was originally developed for the RAISE (Research to identify, optimize and personalize early treatment for people affected by schizophrenia) study (Mueser et al., Psychiatric Services 2015; 66:680-690). Counseling will be provided to all subjects. Counseling is not manualized and no fidelity check is planned. Counseling will focus on:

1) substance abuse counseling to encourage a reduction in or abstinence from alcohol consumption;

2) Medication management counseling to encourage compliance with the treatment.

Efficacy Assessments

Timeline Follow-back (TLFB): Substance use will be recorded using the timeline follow-back method at every study visit. At screening visit, TLFB will assess substance use and dollar amount spent on substances for the past 30 days. All other visits will collect substance use data and dollar amount spent in the past week or for the period between the last visit and the current visit. The subject's drug screen results will be conveyed to the subject prior to administration of the TLFB. If the subject's self-report is at odds with the drug screen results, then the subject's report will not be challenged. All reported data from the subject and drug test results will be collected and used in exploratory analyses

Visual Analog Scale (VAS): The VAS will be used to assess craving for substance use as per the schedule of events and administered as per the schedule of events. The VAS is a horizontal line with a unipolar scale, anchored on the right side with

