Study intervention: Brexpiprazole switch: For the brexpiprazole group, an overlap and taper switch method will be used. The current antipsychotic medication will be tapered following standard clinical practice and discontinued over a time period of 6 weeks. Brexpiprazole will be started at 1mg/day for 4 days, and 2mg/day for 3 days, and then titrate by up to 1mg/day increase every 3 days to reach 4mg/day, or as much and as fast as the participant can tolerate. Participants will stay on 4mg/day or the highest tolerable dose until the end of the study.

Medication adherence will be measured via pill counts at weekly visits. The study staff will discuss pill count data with participants to emphasize the need to take the study medication.

If participants cannot tolerate brexpiprazole after randomization, it will be stopped, though the participant may continue to be followed on another treatment (ideally their pre-study antipsychotic medication) for the remaining weeks of the study. The subject will then continue the rest of the study on their previous antipsychotic medication.

The following assessments will be completed at baseline visit:

- 1) Anthropometric measures (weight, waist circumference and height at screening to be used) and Vital signs
- 2) Weekly TLFB
- 3) Drug screen
- 4) Post-Screening Pregnancy Checklist
- 5) AE review
- 6) PANSS, SANS, QLS, CGI-S
- 7) C-SSRS, EPS scales, CDRS
- 8) Supportive counseling

Week 6 and week 12 visits: The following assessments will be done at week 6 and 12.

- 1) Anthropometric measures (weight, waist circumference) and Vital signs
- 2) Weekly TLFB
- 3) Drug screen
- 4) Post-Screening Pregnancy Checklist (Week 6 only)
- 5) AE review
- 6) PANSS, SANS, QLS, CGI-S
- 7) C-SSRS, EPS scales, CDRS
- 8) Supportive counseling
- 9) ECG
- 10)Labs (CMP, CBC, lipid panel)
- 11)Labs hs-CRP, IL-6 and TNF-alpha collected and stored at -80F
- 12)Fagerstrom test

Week 2, 3,4,5,7,8,9,10,11 visits: These visits may be completed virtually through a secured platform depending on the most current COVID situation. During the virtual routine follow up visits, vital signs and urine drug screen will be unable to be collected; but all subjects who go through the switch will have demonstrated no clinically significant changes in vitals, ECG, or lab results in prior long visits. The following assessments will be administered at these weekly visits:

- 1) Vital signs and anthropometric measures (weight)
- 2) Urine drug screen

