The study will be conducted as per the protocol and will adhere to the GCP standards. The investigators and all study staff should be trained in GCP guidelines.

Informed Consent

The PI must ensure to clearly explain and provide oral and written information on the study purpose, procedures, risks and benefits of participating (including potential risks involving the study medications) to each subject and/or legal guardian. All information should be provided in language that is easy to understand. All subjects must be informed that their participation is voluntary and they can withdraw from the study at any time if they choose. If the subject chooses to participate, he/she or legal guardian must sign the informed consent form and when required, the caregiver must sign the caregiver ICF. Any questions, concerns, or ambiguities will be clarified by the site's PI or another study clinician prior to the patient signing consent.

L. STATISTICS AND DATA ANALYSIS

Intent-to-treat analysis and a mixed model approach will be conducted to estimate the pragmatic effects of brexpiprazole treatment on the number of days of substance use in the past week, substance craving, psychiatric symptoms and quality of life. The entire 12 week duration of treatment, including the 6-week switchover phase, will be included in the analysis. Polynomial time trends (e.g., slopes) will be used to fit the population mean response curve for the control group. Group-by-time interactions will be modeled as a function of time to fit between-group effects. Subject-specific parameters will be estimated to model individual subject deviations from the group mean. Baseline measures of substance use and clinical symptoms will also be included in the model as covariates.

REFERENCES

3. van Dijk D, Koeter MW, Hijman R, Kahn RS, van den Brink W. Effect of cannabis use on the course of schizophrenia in male patients: a prospective cohort study. Schizophr Res. 2012; 137(1-3): 50-7.

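### The covariate rule leaves out baseline craving for the second primary outcome although the VAS is scheduled twice before treatment; how much precision this costs depends on model choices that Section L leaves open

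*Combined protocol and SAP*

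**What the plan says.** Section L has one model paragraph for all outcomes, and the synopsis carries essentially the same text. The outcomes are "the number of days of substance use in the past week, substance craving, psychiatric symptoms and quality of life". The covariate rule is: "Baseline measures of substance use and clinical symptoms will also be included in the model as covariates". It names neither craving nor quality of life.

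Craving is not a sub-item of substance use. Section C makes it the second primary objective, to "examine the effect of brexpiprazole treatment on substance craving using" the VAS, separate from the days-of-use objective measured by the TLFB. It does not plainly fall under clinical symptoms either, because the synopsis defines psychiatric symptoms by the PANSS, SANS, CDRS and CGI.

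On timing, Section E says "The VAS will be used to assess craving for substance use as per the schedule of events". Table 1 marks the VAS in all 15 columns: screening, week 0, weeks 1 to 12 and early termination. The Section F visit descriptions, including the list headed "The following assessments will be completed at baseline visit", do not mention the VAS.

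On the treatment effect: "Group-by-time interactions will be modeled as a function of time to fit between-group effects". On random effects: "Subject-specific parameters will be estimated to model individual subject deviations from the group mean". Section L includes the whole 12 weeks in the analysis. It does not say whether the week 0 value is a response, whether a group main effect is fitted, or whether the tested contrast is a slope, a week-12 difference or an average.

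**The concern.** An outcome's own pre-treatment value is usually a strong candidate covariate for it. On the words of Section L, the model for a primary outcome is adjusted for other baseline measures but not for craving itself, while two suitable readings are already scheduled. In a trial that randomizes 50 and expects 40 completers, stable between-subject differences in VAS scoring and chance imbalance in starting craving can make up a large part of the error of a group comparison. If the model removes neither, the craving result is less precise than the collected data allow.

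**Working it through.** **The plan's own figure.** Section D: 40 completers at 20% discontinuation needs 40 / 0.8 = 50 randomized. This reproduces. No power, effect size, alpha, VAS standard deviation, allocation ratio or correlation is stated.

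**Assumptions for illustration.** 1:1 allocation, n = 20 completers per arm, VAS SD = 1, linear time trend, compound symmetry with correlation ρ between any two readings, ρ = 0.3, 0.5, 0.7, and no other covariates unless stated.

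**Week-12 contrast, responses at weeks 1 to 12, group main effect fitted.** The variance is (2/n)[B + (1 − ρ)h]. Here h = 1/12 + (12 − 6.5)²/143 = 0.295 is the leverage of week 12. B is the between-subject variance: ρ without baseline craving, and ρ − ρ² with one pre-treatment VAS as covariate.

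- At ρ = 0.5, without: 0.1 × (0.5 + 0.5 × 0.295) = 0.0647, SE 0.254.
- At ρ = 0.5, with: 0.1 × (0.25 + 0.5 × 0.295) = 0.0397, SE 0.199.

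**Slope contrast, same model.** The variance over 12 weeks is (2/n)(1 − ρ) × 144/143. B drops out, so the covariate cannot change it.

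**Week 0 also a response.** Generalized least squares on weeks 0 to 12, with and without a group main effect.

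| Reading of Section L | SE at ρ = 0.3 / 0.5 / 0.7 |
|---|---|
| Weeks 1–12, group main effect, week-12 contrast, no baseline craving | 0.225 / 0.254 / 0.281 |
| Same, one pre-treatment VAS as covariate | 0.204 / 0.199 / 0.173 |
| Week 0 as response, group main effect, week-12 contrast | 0.222 / 0.252 / 0.280 |
| Weeks 1–12, group main effect, slope contrast, with or without the covariate | 0.265 / 0.224 / 0.174 |
| Weeks 1–12, group-by-time only, no baseline craving | 0.211 / 0.199 / 0.164 |
| Week 0 as response, group-by-time only | 0.200 / 0.183 / 0.148 |
| Same, screening VAS added as covariate | 0.191 / 0.172 / 0.138 |

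**Reading the table.**

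- First to second row: 1 − 0.204/0.225 = 9%, 1 − 0.199/0.254 = 22%, 1 − 0.173/0.281 = 38%. Under compound symmetry the screening VAS used alone gives the same cut as the week 0 VAS.
- Third row: making week 0 a response recovers almost nothing while a group main effect is fitted.
- Sixth row: with the group effect carried only by group-by-time, the SEs equal those of the matching model with week 0 as covariate, so no week 0 information is lost. Adding the screening VAS cuts the SE by about 4% to 7% (for example 1 − 0.172/0.183 = 6%).

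**Two checks on the largest effect.**

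- Planned covariates: represent them by one proxy correlated 0.2, 0.4 or 0.6 with craving. For a single week-12 value at ρ = 0.5, baseline craving then removes a further 23%, 16% or 5% of the residual variance, against 25% with no proxy. Over all nine combinations of ρ and proxy correlation the range is 1% to 47%.
- Random slopes: adding a slope variance of 0.003 per week² changes the first two rows to 0.306 / 0.329 / 0.349 and 0.291 / 0.288 / 0.270, so the cuts shrink to about 5%, 12% and 23%.

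**The case against.** The strongest reply is that absence from the covariate list is not absence from the model. Section L describes a longitudinal mixed model, does not exclude week 0 from the response, and describes the group difference through group-by-time terms. Read literally, with week 0 as a response and no group main effect, the week 0 VAS is already fully used. This stands, and it rules out a stronger inference that a reader might draw: that the craving comparison certainly loses precision. The plan does not state that reading, however. If a group main effect is added and week 12 is tested, week 0 as a response gives almost no protection.

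A reader might also apply the single-time-point factor 1 − ρ² and claim a large power gain. The documents do not support that. Section L does not specify a single-time-point comparison, no power target exists as a benchmark, and the planned covariates may already take part of the gain. That those covariates predict craving less well than earlier craving does is plausible, but no figure in the documents shows it.

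The week 0 VAS also needs care. Under Section F the condition is generated once eligibility is confirmed and is accessible to the site. No blinding is described, and subjects will know whether they are switching. The order of VAS and disclosure at the baseline visit is not given, so this self-report may follow knowledge of assignment. The screening VAS precedes randomization. Finally, that two readings are taken rests on Table 1 alone.

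**Conclusion.** The omission is real: the stated rule gives the craving model no own-baseline covariate, and it does the same to quality of life. The loss is conditional. It is about 9% to 38% of the SE for a week-12 contrast with a group main effect, and generally smaller with the planned covariates or random slopes. It is about 4% to 7% if week 0 is a response with a common starting mean, and nil for a weeks 1–12 slope contrast with a group main effect. All these sizes rest on an assumed correlation and covariance, because the documents give neither. The point merits a change because it concerns a primary outcome in a small trial and uses readings already scheduled. It does not show that the planned analysis is invalid.

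**What to change.** In Section L and the synopsis:

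1. State that each outcome's own pre-treatment value enters its model, either as a covariate or as a week 0 response with a common starting mean, and never both. Apply this to quality of life too, which Table 1 schedules only once before treatment.
2. For craving, include the screening VAS as a covariate. Use the week 0 VAS as well only if it is recorded before assignment is disclosed. A common starting mean is justified only on that condition.
3. Say whether a group main effect is fitted, and name the tested contrast.
4. Reconcile Table 1 with the Section F visit lists on when the VAS is taken, and state its order relative to disclosure at the baseline visit.

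The cost is a few sentences and about one degree of freedom in the model. No assessment is needed beyond those in Table 1.
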